regimen but with less side effects and more efficacious platelet inhibitory effects than clopidogrel, including after PCI [1,20]. All patients will maintain aspirin 81 mg/qd at least for the duration of hospital stay. Aspirin therapy will be discontinued at time of hospital discharge or at 7 days after PCI at the discretion of the treating physician in patients deemed to be at high ischemic risk, as per standard of care for patients requiring concomitant treatment with a P2Y₁₂ inhibitor and an OAC [14,15].

Assigned treatment will be maintained for 30±5 days. PD assessments will be conducted at 3 time points: i) baseline (while on standard of care DAPT therapy): day after PCI, ideally before the administration of the morning dose of P2Y₁₂ inhibiting therapy and OAC (trough levels of platelet reactivity); however, since patients may get discharged the same day of the PCI or may have already taken their daily dosing regimen, blood sampling will be allowed as this does not interfere with the study hypothesis; patients will continue to take their morning dose of aspirin and all other standard of care therapies; ii) 30±5 days after randomization: before (trough levels of platelet reactivity) and 2 hours after (trough levels of platelet reactivity) the administration of the morning doses of P2Y₁₂ inhibiting therapy and OAC (trough levels of platelet reactivity); patients will take all other standard of care therapies. Figure 2 illustrates the overall study design and a further breakdown of what will occur during the course of the study:

- Patients will first be screened by research personnel to see if they are eligible for the study. Results from blood tests performed within the last 30 days which patients would have performed because of their stent procedure will be considered valid for screening purposes.
- If it is a woman of childbearing potential, a pregnancy test will be done. If the subject is found to be pregnant, their participation in this study will end.
- If they are eligible for the study based on the screening results, they will start the study procedures as outlined below:
 - Genetic test buccal swab. This swab is being done to determine CYP2C19 genetic status.
 - The physician will determine the ABCD-GENE score as described in Figure
 1. This score is calculated by looking at the subject's CYP2C19 genetic

status and clinical information, including age, BMI, renal function, and diabetic status.

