- 5) *T-TAS*: T-TAS is an automated microchip flow chamber system for the quantitative analysis of the thrombus formation process under blood flow conditions. T-TAS allows measurement of thrombus formation using the PL/AR-chips (Diapharma, West Chester Township, OH) [17-18]. The PL/AR-chips contains 25 capillary channels (width 40 μm, depth 40 μm) coated with type I collagen and is specifically designed for quantitative analysis of platelet thrombus formation, including platelet adhesion and aggregation, granule secretion, and thrombus growth in the absence of coagulation and fibrinolysis systems. In measurements using the PL/AR-chips, a blood sample collected in a hirudin and sodium citrate containing blood sampling tube. The platelet aggregates gradually increase in size and, in the process, occlude the capillary, resulting in an increase in flow pressure. In the present study, total platelet-derived thrombogenicity is expressed as the area under the flow pressure curve for the first 10 min for the PL/AR-

chips tested at a flow rate of 18 μ L/min (PL18-AUC10). Low PL18-AUC10 reflect reduced thrombus growth and rapid breakdown of the thrombus.

Study endpoints, sample size calculation and statistical analysis

The primary end point of our study will be levels of platelet reactivity, measured as PRU using the VN system, of ticagrelor versus clopidogrel at 30 days after randomization in patients with an ABCD-Gene score ≥ 10 . We hypothesize that ticagrelor 60 mg bid will lead to lower PRU compared with clopidogrel 75 mg qd. Based on previous studies [20], assuming a standard deviation of 55 and 80 PRU for ticagrelor and clopidogrel, respectively, a sample size of 17 patients per treatment group with valid primary end point data will be required to detect an absolute difference of 90 PRU between ticagrelor and clopidogrel with a 90% power and a 2-tailed alpha value of 0.05. Assuming a potential 25% in data attrition due to patient drop-out (e.g., due to side effects, unplanned use of parenteral antiplatelet therapies after randomization or withdrawal of consent) or invalid PD samples (e.g., due to hemolysis or technical reasons), a sample size of up to 21 patients per randomized group; 42 total will be randomized and an additional 42 in the control group. Thus, considering the 3 treatment arms, a total of up to 84 patients are expected to be enrolled to reach the sample size of patients with valid primary end point data required for the primary end point.

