Additional exploratory end points will include the comparisons between clopidogrel-treated patients with ABCD-Gene score<10 and the other 2 arms, as well as comparisons between groups of rates of HPR. For baseline characteristics, categorical variables will be expressed as frequencies and percentages; continuous variables will be

presented as mean ± SD or median [IQR]. Continuous variables will be analyzed for normal distribution with the Kolmogorov-Smirnov test. Comparisons for the primary end point as well as for other intergroup comparisons of continuous variables will be performed with an analysis of covariance with a general linear model with baseline value of the corresponding platelet function test as a covariate. Intragroup comparisons will be performed using a mixed linear model. Comparisons for categorical variables, including rates of HPR will be performed with the Chi square test or Fisher exact test. A p-value < 0.05 will be considered statistically significant. Statistical analysis will be performed with SPSS version 25 software (SPSS Inc.). Data analysis will be performed at the University of Florida. Data transfer will occur in a HIPAA de-identified manner. Data from The Netherlands will arrive coded so that source of data can be easily known."

The PD population will include all patients with PD data and without a major protocol deviation thought to affect significantly the PD of ticagrelor or clopidogrel. The PD population will be used for analysis of all primary and secondary PD variables. Erroneously treated patients (eg, those randomized to one treatment but actually given the other) will be accounted for based on the actual treatment received.

All patients who received at least 1 dose of study drug will be included in the safety population. Safety will be evaluated by assessment of adverse events (including bleeding and ischemic). Adverse events will be collected up to completion of the study. Bleeding events will be classified according to BARC (Bleeding Academic Research Consortium) criteria [27]. Stent thrombosis will be classified according to ARC (Academic Research Consortium) definitions [28]. MI, including peri-procedural MI, will be defined according to the universal definition [29]. Ischemic stroke will be defined as

an ischemic cerebral infarction caused by an embolic or thrombotic occlusion of a major intracranial artery. Death will be considered cardiac in origin unless obvious non-cardiac causes can be identified.

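### The primary ANCOVA has no rule for a missing baseline PRU, so run as written it would omit randomised patients who have a valid day-30 PRU: a small, avoidable loss of precision

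*Combined protocol and SAP*

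**What the plan says.** All of this is in Section 6 of the combined protocol and SAP.

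- **Endpoint.** The primary endpoint is "levels of platelet reactivity, measured as PRU using the VN system, of ticagrelor versus clopidogrel at 30 days after randomization". The comparison is confined to the randomised high-score cohort (ABCD-GENE 10 or more). It is a day-30 measurement; baseline PRU is not part of it.
- **Model.** The primary and other between-group comparisons of continuous variables use an analysis of covariance with a "general linear model with baseline value of the corresponding platelet function test as a covariate", run in SPSS 25.
- **Sample size.** The plan states that "a sample size of 17 patients per treatment group with valid primary end point data will be required". It then allows 25% attrition for drop-out or "invalid PD samples (e.g., due to hemolysis or technical reasons") and arrives at up to 21 randomised per arm. The time point of the invalid sample is not specified.
- **Analysis set.** "The PD population will include all patients with PD data and without a major protocol deviation" thought to affect the pharmacodynamics of either drug. The section does not say which PD data a patient must have.
- **Baseline draw.** Under Study design, the draw is planned for the day after PCI, ideally before the morning dose. However, "since patients may get discharged the same day of the PCI or may have already taken their daily dosing regimen", sampling outside that ideal is permitted.

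The plan gives no imputation rule, no fallback model and no requirement for a valid baseline PRU before randomisation.

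**The concern.** A general linear model uses only rows in which every covariate is present. A patient therefore needs two valid VerifyNow results to count in the primary analysis, although only the day-30 one is the endpoint. A haemolysed or failed baseline sample would discard a primary endpoint that had been observed.

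What is at stake is precision, and a decision left open. With about 17 evaluable patients per arm, each lost patient widens the confidence interval noticeably. Without a rule, the analyst chooses between dropping and keeping such patients after the data are in, in a study that is open-label apart from the laboratory staff. The omission is inferred from the plan's silence together with the stated model; the plan does not state it as a rule.

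**Working it through.** **1. The plan's own figure.** Inputs are stated in the sample size paragraph: "assuming a standard deviation of 55 and 80 PRU for ticagrelor and clopidogrel, respectively", and a design to "detect an absolute difference of 90 PRU between ticagrelor and clopidogrel with a 90% power and a 2-tailed alpha value of 0.05". With normal quantiles, (1.960 + 1.282)² ≈ 10.51.

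- SD 80 in both arms: n = 2 × 80² × 10.51 / 90² = 16.6, so 17. This matches the plan.
- Both stated SDs: n = (55² + 80²) × 10.51 / 90² = 9425 × 10.51 / 8100 = 12.2, so 13 (14 with the t distribution).

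The stated 17 is therefore conservative for its own SDs. The t-based power with SDs 55 and 80 is 0.96 at 17 per arm, 0.95 at 16, 0.93 at 15 and 0.91 at 14.

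**2. Patients analysed per arm.** Assumptions, none of them in the documents: 15% of patients lack a valid day-30 PRU, and 5, 10 or 15% lack a valid baseline, independently. From 21 randomised per arm, 21 × 0.85 = 17.85 have the endpoint.

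| Baseline missing | Analysed as written | Analysed if all valid endpoints are kept | Combined loss as written |
|---|---|---|---|
| 5% | 17.85 × 0.95 = 17.0 | 17.9 | 1 − 0.85 × 0.95 = 19.3% |
| 10% | 17.85 × 0.90 = 16.1 | 17.9 | 1 − 0.85 × 0.90 = 23.5% |
| 15% | 17.85 × 0.85 = 15.2 | 17.9 | 1 − 0.85 × 0.85 = 27.8% |

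The plan's 25% allowance leaves 21 × 0.75 = 15.75 per arm.

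**3. Effect on the standard error.** Let m be the fraction of baselines missing and ρ the baseline-outcome correlation (not given; 0.2 to 0.5 assumed). To a first approximation, the complete-case variance is proportional to (1 − ρ²)/(1 − m). If missing baselines are filled with a common mean, it is proportional to 1 − (1 − m)ρ². The ratio of standard errors is

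√{(1 − ρ²) / [(1 − m)(1 − (1 − m)ρ²)]}.

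- m = 0.05: √[0.96/(0.95 × 0.962)] = 1.02 at ρ = 0.2; √[0.75/(0.95 × 0.7625)] = 1.02 at ρ = 0.5.
- m = 0.10: √[0.96/(0.90 × 0.964)] = 1.05; √[0.75/(0.90 × 0.775)] = 1.04.
- m = 0.15: √[0.96/(0.85 × 0.966)] = 1.08; √[0.75/(0.85 × 0.7875)] = 1.06.

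Simulation with these inputs (8,000 trials per setting, SDs 55 and 80, true difference 90 PRU) gives slightly larger ratios, as expected at this sample size: 1.02 to 1.10 over the whole grid. Both the complete-case and the filled estimate average about −90 PRU.

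**4. Effect on power.** In the same scenarios, complete-case power for 5, 10 and 15% missing is about 0.95, 0.94 and 0.93 at ρ = 0.2, and 0.98, 0.98 and 0.97 at ρ = 0.5. All exceed the planned 0.90.

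**5. Sensitivity to the SD.** Take exactly 17 valid day-30 values per arm, ρ = 0.3 and SD 80 in both arms, the variant that reproduces 17. Simulated power with patients dropped versus kept is 0.87 versus 0.91 at 10% missing, and 0.83 versus 0.90 at 20%. With the stated SDs the same comparison gives 0.94 versus 0.96, and 0.91 versus 0.96.

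**The case against.** The strongest case on the other side has four parts.

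- **The rate is unknown.** No document gives a missing-baseline rate. If every baseline is obtained and valid, the loss is nil. This stands, and every size above is conditional on it.
- **The plan works to obtain baselines.** A reader might take the remark about same-day discharge as a sign that baseline draws will be missed. The sentence says the reverse: those circumstances are the reason sampling outside the ideal window is allowed. VerifyNow is also read within 2 hours of the draw, so a failed sample could be noticed early, though no redraw is promised. This stands for missed draws; haemolysed or failed samples remain possible.
- **The loss may be budgeted.** The 25% allowance covers invalid samples without naming a time point. On that reading, two of the three scenarios (19.3% and 23.5%) fall inside it, and the third exceeds it by about 0.6 patient per arm (15.75 − 15.2). The allowance is, however, tied to valid primary endpoint data, which points to day 30. The text supports either reading, so the overlap cannot be excluded.
- **The analysis set is not contradicted.** A reader might infer that the model conflicts with the PD population. The definition does not say which PD data are needed and can mean those the specified analysis requires. It is ambiguous, not contradictory.

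None of this supplies the missing rule.

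**Conclusion.** The gap is real and its importance is low. The primary model needs a baseline PRU, no rule covers its absence, and the default result is to omit patients whose primary endpoint was observed. Under assumed missing-baseline rates of 5 to 15%, 15% loss at day 30 and a correlation of 0.2 to 0.5, the cost is a standard error about 2 to 10% larger than necessary.

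Two stronger conclusions are tempting, and the documents do not support them. The first is that the trial becomes underpowered. With the stated SDs and the losses considered here, power stays at about 0.93 to 0.98. It falls below 0.90 only if the ticagrelor SD of 55 is replaced by 80, which is not what the plan assumes. The second is that the comparison is biased. Baseline is meant to be drawn on standard-of-care therapy, before assigned treatment, so whether it is missing should not depend on arm; in simulation under that condition both estimators centre on the true difference.

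**What to change.** Optional. Add to the statistical analysis text of Section 6, after the ANCOVA sentence:

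*In the randomised comparison of ticagrelor with clopidogrel, every patient in the PD population with a valid day-30 PRU is analysed. A missing or invalid pre-treatment baseline PRU is replaced by the mean of the observed baseline values pooled over both randomised arms. An ANCOVA restricted to patients with an observed baseline is a sensitivity analysis.*

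The fill is justified because it ignores treatment assignment and, under randomisation, baseline is independent of arm. It should not be applied to comparisons with the ABCD-GENE<10 cohort, which is not randomised and may differ at baseline. Other prespecified methods that keep these patients, such as a missing-indicator term, would also serve.

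The cost is one SAP sentence group and one extra sensitivity run. No new data or procedures are needed.

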Results from blood tests performed within the last 30 days will be considered valid for screening. Patients will undergo genetic testing to identify CYP2C19 genetic status using the Spartan assay or central lab. Randomization will occur once genetic testing results become available, ideally prior to hospital discharge. However, for patients discharged

[figure not shown]
before having results available or over the weekend they will be allowed to return for their randomization within 3 days from test results. Patients with an ABCD-GENE≥10 score will be randomized in a 1:1 fashion to ticagrelor (60 mg/bid) or clopidogrel (75 mg/qd). Patients with an ABCD-GENE<10 will be treated with clopidogrel (75 mg/qd).

Since the choice of P2Y₁₂ inhibitor during the PCI procedure may vary (commercially available agents include clopidogrel, ticagrelor and prasugrel), the following recommendations will be made based on the agent chosen and the treatment assignment: a) patients assigned to clopidogrel and also treated with clopidogrel during PCI will continue with a 75 mg/qd maintenance dose for the duration of the study; b) patients assigned to clopidogrel but treated with ticagrelor or prasugrel during PCI will receive a 600 mg loading dose clopidogrel followed by a 75 mg/qd maintenance dose for the duration of the study; c) patients assigned to ticagrelor and also treated with ticagrelor during PCI will continue with ticagrelor 60 mg bid maintenance dose for the duration of the study; d) patients assigned to ticagrelor but treated with clopidogrel or prasugrel during PCI will be administered a 180 mg loading dose followed by a 60 mg bid for the duration of the study. Administration of randomized treatment will occur prior to hospital discharge as would occur per standard of care for administration of the next dose of P2Y₁₂ inhibiting therapy. The use of a loading dose when switching agent is in line with consensus recommendations for switching P2Y₁₂ inhibiting therapy [19]. The clopidogrel 600mg loading dose and 75 mg/qd maintenance dose regimen is in line with practice recommendations [1]. The ticagrelor 180 mg loading dose regimen is in line with practice guidelines; the 60 mg bid maintenance dose regimen was chosen in light of recent data that this dose provides platelet inhibitory effects not dissimilar from the 90 mg bid dosing

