Patients with an ABCD-GENE<10 will be treated with clopidogrel (75 mg/qd). Patients with an ABCD-GENE≥10 score will be randomized in a 1:1 fashion to ticagrelor (60 mg/bid) or clopidogrel (75 mg/qd). Assigned treatment will be maintained for 30 +/- 5 days.

Blood will be collected at two visits by inserting a needle into a vein or from a catheter in a vein. The first visit will be after the PCI ideally before the subject has taken their antithrombotic medications (baseline); however, since patients may get discharged the same day of the PCI or may have already taken their daily dosing regimen, blood sampling will be allowed as this does not interfere with the study hypothesis. The second visit will be 30 +/- 5 days later. At this visit there will be two blood draws: the first before the subject has taken their antithrombotic medication (trough) and second 2 hours after the subject has taken their antithrombotic medication (peak).

PD measures will include a multitude of assays aimed to assess various measures of platelet reactivity, including purinergic and non-purinergic signaling pathways, and thrombin generation, as described below. Although the study will have an open-label design, laboratory personnel will be blinded to treatment assignments. Compliance with antithrombotic therapies will be assessed by interview and pill counting. During study treatment, major adverse cardiac events (death, myocardial infarction, stroke, and urgent revascularization procedures), serious adverse events (bleeding and other adverse events),

as well as non-serious adverse events will be collected. After completing the study, patients will resume an antithrombotic treatment regimen at the discretion of the treating physician.

Study population

A total of 84 CAD patients will be recruited In particular, 42 patients with an ABCD-GENE≥10 will be included and randomized to ticagrelor (n=20) or clopidogrel (n=20), while 42 patients will be in the ABCD-GENE<10 cohort. Patients will need to meet the following study entry criteria:

Inclusion criteria:

- Age \geq 18 years
- Willing and able to provide written informed consent
- Undergone successful PCI and treated with DAPT (aspirin plus a P2Y12 inhibitor) per standard of care
- On treatment with a novel oral anticoagulant (apixaban, dabigatran, edoxaban, or rivaroxaban) for any indication (dosing regimen will be according to standard of care and at the discretion of the treating physician)

Exclusion criteria:

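### The 0.05 significance rule covers every comparison, although only one PRU comparison is powered and the randomised secondary readouts carry no exploratory label

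*Combined protocol and SAP*

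**What the plan says.** All references are to section 6, Research Plan, of the combined protocol and SAP.

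- **Primary end point.** The subsection on study endpoints, sample size and statistical analysis names one: PRU at 30 days, ticagrelor versus clopidogrel, in the cohort scoring 10 or more. It is sized "with a 90% power and a 2-tailed alpha value of 0.05".
- **Exploratory end points.** The same subsection gives this label to comparisons of the cohort scoring below 10 with the other two arms, and to HPR rates.
- **Methods.** Analysis of covariance is used for the primary and for all other between-group comparisons of continuous variables, mixed models within groups, and chi-square or Fisher tests for categorical variables. One rule then closes the list: "A p-value < 0.05 will be considered statistically significant". There is no adjustment, no order of testing, and no statement that any p-value is descriptive.
- **Secondary variables.** The next paragraph says "The PD population will be used for analysis of all primary and secondary PD variables". No secondary variable is listed anywhere.
- **Breadth of testing.** The Study design subsection says "PD measures will include a multitude of assays aimed to assess various measures of platelet reactivity" and provides two blood draws at the day-30 visit.

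**The concern.** The rule makes no distinction between the one comparison the study was sized for and everything else. Calling an end point exploratory normally tells the reader that its p-value is not evidence on the same footing as the primary. Here the label is followed by a rule that treats all p-values alike. The randomised comparisons on the other assays do not carry even the label; they appear to be the undefined secondary variables.

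Several of these readouts look at pathways other than P2Y12, and Study design says the assays cover non-purinergic signalling as well. A true absence of difference is therefore plausible for some of them. Section 8, Possible benefits, says that differences in antiplatelet profile may prompt further study. A chance result on, say, TRAP aggregation or clot lysis, reported as significant under the plan's own rule, could misdirect that work.

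**Working it through.** **1. The plan's own figure.** The plan works from "assuming a standard deviation of 55 and 80 PRU for ticagrelor and clopidogrel, respectively", and 17 per group "will be required to detect an absolute difference of 90 PRU between ticagrelor and clopidogrel". By the normal approximation with a common SD of 80, n = 2 × (1.960 + 1.282)² × 80² / 90² = 2 × 10.51 × 0.790 = 16.6, so 17 per group. This reproduces the stated figure. With the two SDs as stated, n = 10.51 × (55² + 80²) / 90² = 12.2, so 13 (14 with a Welch t-test), and power at 17 is 95.8%. The 17 is thus adequate for one test at two-sided 0.05, and that is the only test it was derived for.

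**2. Continuous readouts per draw** (Description of laboratory assays).

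| Assay | Readouts |
|---|---|
| VerifyNow PRU | 1 |
| Aggregometry: arachidonic acid, collagen, TRAP, ADP, and the combined agonist (CAT) | 5 |
| VASP index | 1 |
| Clot assay: 4 parameters × 1 or 2 activators | 4 or 8 |
| T-TAS | 1 |
| Total | 12 or 16 |

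The range for the clot assay arises because the text joins the two activators with *or*.

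**3. Tests in the randomised contrast.** Readouts × draws = 12 × 2 = 24 to 16 × 2 = 32, including the primary. Testing every readout at both draws is an assumption, since the plan lists no tests. None of the other 23 to 31 is labelled exploratory.

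**4. Expected false positives.** Expected count = 0.05 × number of true nulls; correlation between tests does not change it. Only readouts for which no drug difference is plausible should be counted.

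| Readouts assumed not to differ (randomised contrast) | Tests | Expected false positives |
|---|---|---|
| Arachidonic acid, collagen, TRAP and clot parameters: (3 + 4 or 8) × 2 draws | 14–22 | 0.7–1.1 |
| The same, one draw only | 7–11 | 0.35–0.55 |
| Adding CAT and T-TAS: (5 + 4 or 8) × 2 draws | 18–26 | 0.9–1.3 |

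For the first row, the chance of at least one is 1 − 0.95^14 = 51% to 1 − 0.95^22 = 68% if the tests were independent. They are not: both draws come from the same patients and the clot parameters from one assay. These percentages are therefore only a guide.

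**5. Is the primary one test?** The endpoint text does not say which day-30 draw supplies the primary PRU. The paragraph on time points in Study design labels both day-30 draws as trough; the later description of the two visits labels them trough and peak. If either draw could serve, the error rate for the primary could reach 1 − 0.95² = 9.75% with independent tests, and less if they are positively correlated.

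**The case against.** This is a small pharmacodynamic study with one primary end point, and nominal p-values for supporting assays are common practice. Other tests do not inflate the primary's type I error. That stands, provided the primary is a single named test. The list of exploratory end points is also worded as open-ended, so the sponsor might say that it covers the remaining assays. But the plan then speaks of secondary variables, and no reading of the label limits the significance rule.

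A reader might infer something stronger: about 100 tests and several false findings. Counting three group contrasts and three HPR definitions does give (12 + 3) × 2 × 3 = 90 to (16 + 3) × 2 × 3 = 114 tests, and 0.05 × 90 = 4.5 to 0.05 × 114 = 5.7 false positives if every null were true. The documents do not support this as a forecast:

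- Of those tests, 66 to 82 are already labelled exploratory: 48 to 64 continuous contrasts with the lower-score cohort plus 18 HPR tests.
- The plan itself expects ticagrelor to lower PRU, so the other P2Y12 readouts (ADP aggregation, VASP, HPR rates) cannot reasonably all be null.
- Contrasts with the lower-score cohort are not randomised. The cohorts are defined by age, BMI, kidney function, diabetes and CYP2C19 genotype, so a small p-value there may reflect confounding or a real difference, not chance.
- At one draw only, the total would be 45 to 57.

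**Conclusion.** The point holds as a reporting defect of modest size. As written, the plan would call any result below 0.05 significant, including unpowered randomised comparisons that have no stated status. In that contrast about one false significant effect is to be expected (0.7 to 1.1). This assumes that every readout is tested at both day-30 draws and that the drugs do not differ on arachidonic acid, collagen and TRAP aggregation or on the clot parameters. Within-group tests fall under the same rule and are not counted. It would be wrong to conclude that the primary analysis is compromised: its alpha and sample size stand once the day-30 draw is fixed. Not naming that draw is the one gap that touches the confirmatory test.

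**What to change.** 1. Name the single day-30 draw that supplies the primary PRU, and reconcile the two descriptions of the draws in Study design.
2. List the secondary pharmacodynamic variables.
3. Replace the significance sentence by: *Statistical significance (two-sided 0.05) is declared only for the primary end point. All other PD and HPR comparisons, including the secondary PD variables, are exploratory and are reported as estimates with 95% confidence intervals and nominal p-values.*
4. Add that contrasts with the cohort scoring below 10 are also non-randomised.

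This costs wording only. The primary alpha stays at 0.05 and the 17 per group does not change. The downside is that secondary assay results can no longer be presented as significant findings.
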